8.3 Collection of adverse events

The Principal Investigator is responsible for ensuring that all staff involved in the study are familiar with the content of this section

The definitions of an AE or SAE can be found in [Appendix B](#).

AE will be reported by the patient (or, when appropriate, by a caregiver, surrogate or the patient's legally authorised representative).

The investigator and any designees are responsible for detecting, documenting, and recording events that meet the definition of an AE or SAE. For information on how to follow/up AEs see Section [8.3.3](#).

8.3.1 Method of detecting AEs and SAEs

Care will be taken not to introduce bias when detecting AEs and/or SAEs. Open-ended and non-leading verbal questioning of the patient is the preferred method to inquire about AE occurrences.

8.3.2 Time period and frequency for collecting AE and SAE information

AEs and SAEs will be collected from time of signing of the main study ICF throughout the treatment period and including the follow-up period. The follow-up period is defined as 28 ± 7 days after study treatment is discontinued.

Procedure-related AEs and SAEs for those patients who provide a new tumour sample occurring up to and including 21 days after the new tumour sample collection procedure will be captured. This procedure may be performed prior to signing the main study ICF.

All SAEs will be recorded and reported to the sponsor or designee within 24 hours, as indicated in Section [8.4.1](#). The investigator will submit any updated SAE data to the sponsor within 24 hours of it being available. SAEs will be reported according to local regulations.

Investigators are not obligated to actively seek AE or SAE in former study patients. However, if the investigator learns of any SAE, including a death, at any time after a patient's last visit and he/she considers the event to be reasonably related to the study treatment or study participation, the investigator may notify the sponsor.

The method of defining, evaluating, and assessing causality of AE and SAE are provided in [Appendix B](#).

8.3.3 Follow-up of AEs and SAEs

After the initial AE/SAE report, the investigator is required to proactively follow each patient at subsequent visits/contacts. All AEs and SAEs, will be followed until resolution, stabilisation, the event is otherwise explained, or the patient is lost to follow-up

Any AEs that are unresolved at the patient's last AE assessment in the study are followed up by the investigator for as long as medically indicated, but without further recording in the eCRF. AstraZeneca retains the right to request additional information for any patient with ongoing AE(s)/SAE(s) at the end of the study, if judged necessary.

8.3.4 Adverse event data collection

The following variables will be collected for each AE:

- AE (verbatim)
- The date and time when the AE started and stopped
- The maximum on-treatment CTCAE grade (according to CTCAE version 5.0)
- Whether the AE is serious or not
- Investigator causality rating against the IP(s) (yes or no)
- Action taken with regard to IP(s)
- Outcome

In addition, the following variables will be collected for SAEs:

- Date AE met criteria for SAE
- Date investigator became aware of SAE
- AE is serious due to
- Date of hospitalisation
- Date of discharge
- Probable cause of death
- Date of death
- Autopsy performed
- Causality assessment in relation to study procedure(s)
- Causality assessment to other medication

8.3.5 Causality collection

The investigator will assess causal relationship between each IP and each AE, and answer 'yes' or 'no' to the question 'Do you consider that there is a reasonable possibility that the event may have been caused by the investigational products?'.

For SAEs, causal relationship will also be assessed for other medication and study procedures. Note that for SAEs that could be associated with any study procedure the causal relationship is implied as 'yes'.

A guide to the interpretation of the causality question is found in [Appendix B](#) to the Clinical Study Protocol.

8.3.6 Adverse events based on signs and symptoms

All AEs spontaneously reported by the patient or care provider or reported in response to the open question from the study site staff: 'Have you had any health problems since the previous visit/you were last asked?' or revealed by observation will be collected and recorded in the eCRF. When collecting AEs, the recording of diagnoses is preferred (when possible) to recording a list of signs and symptoms. However, if a diagnosis is known and there are other signs or symptoms that are not generally part of the diagnosis, the diagnosis and each sign or symptom will be recorded separately.

8.3.7 Adverse events based on examinations and tests

The results from the Clinical Study Protocol mandated laboratory tests, ECGs and vital signs will be summarised in the Clinical Study Report. Deterioration as compared with baseline in protocol-mandated laboratory values and vital signs should therefore only be reported as AEs if they fulfil any of the SAE criteria or are the reason for discontinuation of treatment with the IP.

If deterioration in a laboratory value/ECG/vital sign/other safety assessment is associated with clinical signs and symptoms, the sign or symptom will be reported as an AE and the associated laboratory result/ECG/vital sign will be considered as additional information. Wherever possible the reporting investigator uses the clinical, rather than the laboratory term (eg, anaemia versus low haemoglobin value). In the absence of clinical signs or symptoms, clinically relevant deteriorations in non-mandated parameters should be reported as AE(s).

Deterioration of a laboratory value, which is unequivocally due to disease progression, should not be reported as an AE/SAE.

Any new or aggravated clinically relevant abnormal medical finding at a physical examination as compared with the baseline assessment will be reported as an AE unless unequivocally related to the disease under study, see Sections [8.3.9](#) and [8.3.10](#).

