8.3.13 Adverse events of special interest

AESIs are events of scientific and medical interest specific to the further understanding of the study treatment safety profile and require close monitoring and rapid communication by the investigators to AstraZeneca. An AESI can be serious or non-serious. All AESIs will be recorded in the eCRF within 24 hours. Serious AESIs will be recorded and reported as per Section 8.4.1. The rapid reporting of AESIs allows ongoing surveillance of these events in order to characterise and understand them in association with the use of a study treatment.

AESIs will be recorded in the eCRF using a recognised medical term or diagnosis that accurately reflects the event. AEs will be assessed by the Investigator for severity, relationship to the study treatment, possible aetiologies, and whether the event meets criteria for an SAE and therefore requires immediate notification to AstraZeneca. If an AESI evolves into a condition that meets the regulatory definition of “serious” it will be reported on the SAE Report Form.

Based on the available preclinical and clinical data, review of the cumulative literature, reported toxicities for the same class of agents and biological plausibility, reports of hepatotoxicity, hypersensitivity (including anaphylaxis and **CCI** QTc prolongation and pyrexia, for the savolitinib clinical program regardless of seriousness, are to be collected through the clinical study database.

AESIs for osimertinib are ILD or ILD-like adverse reactions (eg, pneumonitis), QTc interval prolongation, keratitis, haematological events, erythema multiforme and SJS, changes in cardiac contractility, and aplastic anaemia. ILD events are to be reported as AEs in the CRF, with additional details captured in the "ILDIS" CRF.

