4.2.3.2 Adverse Event

Key guidelines for counting incidence proportions of adverse events are as follows:

- When a patient has the same AE reported multiple times during an analysis period based on SOC and PT, the patient will only be counted once within a level of MedDRA in an AE incidence table.
- When assessing investigator-reported relationship to study drug of the AEs, if an AE changes in causal relationship during an analysis period for a patient, the related event will be chosen. Related AEs will include those reported as related by the investigator and those with a missing relationship. AE with a missing relationship will be presented as related in summary tables but will be presented in the data listing with a missing relationship.
- When summarising intensity of the AEs, if an AE changes in CTCAE grade during an analysis period for a patient, the AE with the maximum CTCAE grade will be chosen. In case the AE term (SOC and PT) is reported more than once, one of them with missing grade, and at least another with non-missing grade, the maximum CTCAE grade will be chosen from the non-missing grade values and the missing grade can be ignored. If all are of missing grade, then the AE severity will be summarised in an additional “Unknown” intensity category.
- When summarising intensity for drug-related AEs, only drug-related AEs will be used in the analysis. If a patient has the same AE reported multiple times during an analysis period for a drug-related AE, the AE with the maximum CTCAE grade will be chosen.

The number and percentage of patients with TEAEs, as classified by SOC and PT, will be summarised for the Safety analysis set:

- Patients with TEAEs and the number of TEAEs
- TEAEs that are causally related to Osimertinib, causally related to Savolitinib, and casually related to either Osimertinib or Savolitinib,
- TEAEs of CTCAE grade ≥ 3
- TEAEs of CTCAE grade ≥ 3 related to Osimertinib or related to Savolitinib
- TEAEs by common frequency ($>5\%$) in descending order
- TEAEs by maximum CTCAE grade
- TEAEs with death outcome
- Non-serious TEAEs that occurred in greater than 5% of patients

- Serious TEAEs
- Serious TEAEs – key patient information
- Serious TEAEs that are assessed by investigator as causally related to Osimertinib, causally related to Savolitinib, and casually related to either Osimertinib or Savolitinib
- TEAEs leading to dose modification of each study treatment

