- TEAEs leading to discontinuation of each study treatment (overall and within the first 6 weeks)
- TEAEs leading to discontinuation of each study treatment - key patient information
- Other significant TEAEs
- Other significant TEAEs leading to discontinuation of each study treatment (overall and within the first 6 weeks)
- TEAEs of special interest
- TEAEs of special interest by CTCAE grade
- TEAEs of special interest leading to discontinuation of each study treatment (overall and within the first 6 weeks)
- Hypersensitivity/anaphylaxis and hepatotoxicity TEAEs of special interest leading to discontinuation of savolitinib (overall and within the first 6, 12 and 24 weeks)

An overall summary table of the number of patients experiencing at least one adverse event will be produced. An overall summary table of the number of AEs will also be provided.

TEAEs in any category, including AESI, TEAEs of CTCAE grade ≥ 3 , deaths, SAEs, TEAEs leading to discontinuation, and other significant TEAEs will be summarised.

AEs occurring prior to first dose of study treatments (i.e., before study Day 1) which subsequently worsen in severity following dosing will be presented in the summary tables. All other AEs occurring prior to first dose of study treatments (i.e., before study Day 1), or after the 35-day follow-up period (28 days allowing for the ± 7 -day window) after discontinuation of study treatments will be listed, but not included in the summaries.

Details of any deaths will be listed for all patients.

All AEs will be listed, and any AEs started on or after a patient took osimertinib after crossing over from 300 mg bid + placebo to 300 mg bid + osimertinib will be flagged.

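### Protocol 8.3.7 and 8.3.13 conflict on whether an asymptomatic, non-serious, laboratory-only AESI is an AE, so those that led to a hold or dose reduction may be under-counted in the AE-based tables

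*Protocol*

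**What the plan says.** **The general rule.** Protocol 8.3.7 notes that mandated laboratory, ECG and vital-sign results will be summarised in the study report. For laboratory and vital-sign results that worsen from baseline, it concludes that they "should therefore only be reported as AEs if they fulfil any of the SAE criteria or are the reason for discontinuation of treatment". ECGs are not named in this restriction. If symptoms accompany the change, "the sign or symptom will be reported as an AE and the associated laboratory result/ECG/vital sign will be considered as additional information". Clinical terms are preferred to laboratory terms. For tests the protocol does not mandate, a clinically relevant deterioration without symptoms is to be reported as an AE.

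**The AESI rule.** Protocol 8.3.13 states: "An AESI can be serious or non-serious. All AESIs will be recorded in the eCRF within 24 hours". Hepatotoxicity is among the savolitinib events that, "regardless of seriousness, are to be collected through the clinical study database". Haematological events are on the osimertinib list. An AESI needs a recognised medical term or diagnosis and an investigator judgement of severity and relationship.

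**The outputs.** SAP 4.2.3.2 plans, among other AE tables, "TEAEs leading to dose modification of each study treatment", "TEAEs of special interest by CTCAE grade" and TEAEs of grade 3 or higher. SAP 3.2.2.3 assigns AEs to AESI categories by MedDRA higher-level and preferred term.

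Sections 8.3.7 and 8.3.13 do not refer to each other, and neither exempts the other's cases.

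**The concern.** Drug-related liver injury and cytopenia are often found by a blood test alone. Protocol 2.3.1 calls hepatotoxicity an important identified risk of savolitinib, and Appendix I manages much of it by withholding and restarting. Under 8.3.7, an asymptomatic case that is neither serious nor the cause of stopping treatment yields no AE, even if dosing was interrupted or reduced. Under 8.3.13, the same case is an AESI due within a day.

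A site cannot obey both rules. If sites resolve the conflict differently, AE-based rates for a main safety risk partly reflect how each site read the protocol. The cases most exposed are those that changed dosing without ending it, which are the cases the dose-modification table is meant to show. Without an AE record, the investigator's causality judgement and action taken for that event are also not collected (Protocol 8.3.4 and 8.3.5).

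**Working it through.** The point rests on no sample size, error rate or event count, so there is no arithmetic. The check is to follow each kind of laboratory event through the rules.

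**Step 1. Are the tests mandated?** Yes. Protocol Table 10 lists ALT, AST, ALP and total bilirubin (weekly for the first 10 weeks) and the blood counts. 8.3.7 therefore applies to them.

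**Step 2. Does the protocol foresee laboratory-only holds?** Yes. Appendix I 3.3.1 withholds savolitinib on liver tests alone in several situations. Examples are ALT or AST above 5 x ULN for more than 2 weeks, or 8 x ULN, without bilirubin elevation; above 3 x ULN with bilirubin above 1.5 x ULN; and a rising trend above 3 x ULN. Dosing may then resume at the same or a reduced dose, depending on the bullet and the recovery. Tables 20 and 23 also hold drug for Grade 3 toxicity in general, which can include a cytopenia.

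**Step 3. Does the Hy's Law process catch them?** Only in part. Appendix E creates an SAE when AST or ALT is at least 3 x ULN and bilirubin at least 2 x ULN. An isolated transaminase rise, or one with bilirubin between 1.5 and 2 x ULN, does not meet that definition. It prompts sponsor notification and laboratory data entry, but no AE.

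**Step 4. Follow each case for an abnormality in an 8.3.13 category.**

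| Case | 8.3.7 | 8.3.13 | In AE-based tables if 8.3.7 is followed |
|---|---|---|---|
| Serious, including potential Hy's Law | AE | AESI | Yes |
| Non-serious, IP discontinued | AE | AESI | Yes |
| Non-serious, symptomatic, IP held or reduced | Symptom is the AE | AESI | Symptom appears; it may not code to the AESI category |
| Non-serious, asymptomatic, IP held or reduced | No AE | AESI within 24 h | No |

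The rules give opposite instructions in the last row.

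**Step 5. Can the SAP recover the last row?** Not in the AE tables. AESIs are picked out from coded AE terms, and the grade 3 or higher and dose-modification tables count reported TEAEs.

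**Step 6. What is untouched?** Interruptions and reductions are counted from the treatment logs (SAP 3.2.2.1 and 4.2.3.1). CTCAE grade shifts, changes to grade 3 or 4 and transaminase elevations come from laboratory data (SAP 4.2.3.6). AE tables for discontinuation are complete under either rule. The holds and the grades are thus each visible, but no planned table links a hold to the laboratory event behind it or gives the investigator's attribution.

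**The case against.** The strongest reply is that the two sections can be read together. 8.3.7 restricts the reporting of values, while 8.3.13 asks for a diagnosis and, as the specific rule, should prevail. Protocol 6.6 ties dose modification to the type of AE, and Appendix I 3.3.1 is framed as management of drug-related hepatotoxicity, so a hold under it presupposes an event. 8.3.7 also has a rationale: mandated tests get their own summaries and optional tests do not. The sponsor's expert review for other significant AEs (SAP 3.2.2.3) covers marked laboratory abnormalities and events leading to dose reduction.

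Much of this stands. It shows that a site could report correctly, and it rules out some stronger inferences:

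- A reader might infer that 8.3.7 removes all such events from the tables. It does not, because 8.3.13 separately requires them.
- A reader might add pyrexia, since temperature is a mandated vital sign. Appendix I treats pyrexia as a symptom, so 8.3.6 and the symptom sentence of 8.3.7 make it reportable.
- A reader might take any ALT above 5 x ULN with normal bilirubin as an exposed hold. That bullet requires more than 2 weeks, or 8 x ULN; at lower levels without bilirubin elevation a rising trend or a recurrence is needed.
- A reader might infer that the IDMC sees truncated data. The charter is not available and parts of the oversight text are redacted, so this cannot be verified.

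The reply does not remove the conflict. Neither section says which prevails, and 8.3.7 uses the word only. The expert review is sponsor judgement after the fact and does not supply the investigator's causality assessment.

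**Conclusion.** The point holds for a defined group: asymptomatic, non-serious AESIs seen only as a change in a mandated laboratory test, meaning liver-test rises and cytopenias. For these, 8.3.7 and 8.3.13 give contradictory instructions. Where 8.3.7 is followed, those that led to an interruption or reduction risk omission from three AE-based outputs: special-interest, grade 3 or higher, and dose-modifying TEAEs.

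The size is unknown. The documents give no frequency for such events and no indication of how sites read the rule, so the under-count could be negligible or material. The conclusion assumes that at least some sites apply 8.3.7 literally, and that the eCRF completion instructions, which are not among the documents, do not already settle the matter.

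Efficacy analyses are not affected. This is an inconsistency worth correcting because it concerns an important identified risk. It is not evidence that the safety data as a whole are incomplete.

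**What to change.** **Protocol.** Reconcile the two passages with one sentence in 8.3.7, cross-referring to 8.3.13. It should say that the restriction does not apply to events in an 8.3.13 AESI category, or to laboratory abnormalities that are the reason for interrupting or reducing either IP. Repeat this in the eCRF completion instructions.

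**Data already collected.** Before database lock, match treatment-log interruptions and reductions to CTCAE-graded laboratory abnormalities at the same time. Query the site wherever there is no linked AE.

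**Cost.** One sentence and one query run. Reported AE rates will be somewhat higher. The change concerns reporting only and alters no dosing or clinical rule.

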8.3.8 Hy's law

Cases where a patient shows elevations in liver biochemistry may require further evaluation and occurrences of AST or ALT $\geq 3 \times \text{ULN}$ together with total bilirubin $\geq 2 \times \text{ULN}$ may need to

be reported as SAEs. Please refer to [Appendix E](#) for further instruction on cases of increases in liver biochemistry and evaluation of Hy's Law.

8.3.9 Disease-under study

Symptoms of disease-under study are those which might be expected to occur as a direct result of advanced NSCLC. Events which are unequivocally due to disease under study should not be reported as an AE during the study unless they meet SAE criteria or lead to discontinuation of the IP.

8.3.10 Disease progression

Disease progression can be considered as a worsening of a patient's condition attributable to the disease for which the IP is being studied. It may be an increase in the severity of the disease under study and/or increases in the symptoms of the disease. The development of new or progression of existing metastasis to the primary cancer under study should be considered as disease progression and not an AE. Events, which are unequivocally due to disease progression, should not be reported as an AE during the study.

Progression of the malignancy under study, including signs and symptoms progression, should not be reported as an SAE. Hospitalisation due to signs and symptoms of disease progression should not be reported as SAE.

8.3.11 New cancers

The development of a new cancer should be regarded as an AE and will generally meet at least 1 of the serious criteria. New cancers are those that are not the primary reason for the administration of the study treatment and have been identified after the patient's inclusion in this study. They do not include metastases of the original cancer.

8.3.12 Handling of deaths

All deaths that occur during the study, or within the follow-up period after the administration of the last dose of IP, should be reported as follows:

- Death, which is unequivocally due to disease progression, should be communicated to the study monitor at the next monitoring visit and should be documented in the eCRF module, but should not be reported as a SAE during the study.
- Where death is not clearly due to disease progression of the disease under study the AE causing the death should be reported to the study monitor as an SAE within 24 hours. The report should contain a comment regarding the co-involvement of progression of disease, if appropriate, and should assign a single primary cause of death together with any contributory causes.
- Deaths with an unknown cause should always be reported as a SAE but every effort should be made to establish a cause of death. A post-mortem may be helpful in the

assessment of the cause of death, and if performed a copy of the post-mortem results (with translation of important parts into English) should be reported in an expedited fashion to an AstraZeneca representative within the usual timeframes.

8.3.13 Adverse events of special interest

AESIs are events of scientific and medical interest specific to the further understanding of the study treatment safety profile and require close monitoring and rapid communication by the investigators to AstraZeneca. An AESI can be serious or non-serious. All AESIs will be recorded in the eCRF within 24 hours. Serious AESIs will be recorded and reported as per Section 8.4.1. The rapid reporting of AESIs allows ongoing surveillance of these events in order to characterise and understand them in association with the use of a study treatment.

AESIs will be recorded in the eCRF using a recognised medical term or diagnosis that accurately reflects the event. AEs will be assessed by the Investigator for severity, relationship to the study treatment, possible aetiologies, and whether the event meets criteria for an SAE and therefore requires immediate notification to AstraZeneca. If an AESI evolves into a condition that meets the regulatory definition of “serious” it will be reported on the SAE Report Form.

Based on the available preclinical and clinical data, review of the cumulative literature, reported toxicities for the same class of agents and biological plausibility, reports of hepatotoxicity, hypersensitivity (including anaphylaxis and **CCI** QTc prolongation and pyrexia, for the savolitinib clinical program regardless of seriousness, are to be collected through the clinical study database.

AESIs for osimertinib are ILD or ILD-like adverse reactions (eg, pneumonitis), QTc interval prolongation, keratitis, haematological events, erythema multiforme and SJS, changes in cardiac contractility, and aplastic anaemia. ILD events are to be reported as AEs in the CRF, with additional details captured in the "ILDIS" CRF.

